8.5 Study Termination

NCI, DCP as the study sponsor has the right to discontinue the study at any time.

9. CORRELATIVE/SPECIAL STUDIES

9.1 Rationale for Methodology Selection

The most appropriate biomarker of vaccine efficacy is the immune response. We will measure the major T cell dependent anti-MUC1 antibody IgG isotype that requires MUC1 specific T cells to promote isotype switching by B cells from IgM. We will largely focus on IgG, as that antibody isotype is easier to measure and more reproducibly induced. The biospecimen repository archive will include plasma and PBMC for immunologic and other assays, such as the frequency and quality of antigen-specific T cells induced by the vaccine, and changes in the serum cytokine and chemokine profiles.

The MUC1 ELISA is an established assay that has been used to monitor many clinical trials as well as IgG response in large cohorts of patients on other studies. It has been validated as highly reproducible. The set-up includes positive and negative control anti-MUC1 antibodies that allow comparison of results between different studies. Nevertheless, in this trial, each patient will also be his/her own control as we will compare post-vaccination titers with pre-vaccination baseline. All time points will be assayed simultaneously and multiple times.

Immune Assays: Upon receipt of the overnight shipment or immediately after collection, heparinized blood will be centrifuged over a density gradient (FicoII) to separate the plasma and PBMC. Plasma will be collected, aliquoted, and stored at -20°C. PBMC will be washed several times, aliquoted, slowly frozen to -70 to -80°C in human serum with 20% DMSO and stored in the vapor phase of liquid nitrogen.

Measurement of the vaccine-induced anti-MUC1 IgG will be determined by the Enzyme-Linked Immunosorbent Assay (ELISA) that was established in [name] laboratory and successfully used to measure anti-MUC1 responses in humans and mice. The procedure is as follows: Immulon 4 (Thermo-Fisher Scientific, MA) microtiter plates are coated overnight at 4°C with 1µg of synthetic MUC1 100mer peptide (vaccine antigen) dissolved in 0.9% Dulbecco phosphate buffered saline (PBS). Corresponding control plates receive PBS but no antigen. The plates are washed three times with and incubated with 2.5% bovine serum albumin (BSA) in PBS (PBS-BSA) to fully coat the microtiter plate wells with protein and block non-specific binding. PBS-BSA is removed and plasma diluted in PBS-BSA added to the wells. After one-hour incubation at room temperature the plates are washed five times with PBS with 0.1% tween-20 (Sigma-Aldrich, MO), and alkaline phosphatase-conjugated anti-human IgG secondary antibody (Sigma-Aldrich) in PBS-BSA added. Following one-hour incubation, the plates are washed five times and the substrate, p-nitrophenyl phosphate (Sigma-Aldrich), added to each well. The reaction is terminated after one hour by adding 0.5M NaOH. The results are read at optical density (OD) 405nm on a spectrophotometer. The OD values from the control wells containing no antigen are subtracted from the OD values in test wells coated with peptide. Every sample is assayed multiple times at multiple dilutions, in at least triplicate wells. The results can be expressed wither as OD values or control antibody of a known titer, included in the assay, is used to convert the OD values to titers.

For detecting Myeloid-Derived Suppressor Cells (MDSC), PBMC will be thawed and stained with APC-labeled mouse anti-human CD11b antibody (clone: ICRF44, BD Biosciences), PE-Cyanine 7 (PE-Cy7) labeled mouse anti human CD14 antibody (clone: M5E2, BD Biosciences), PE-labeled mouse anti human CD33 antibody (clone: WM53, BD Biosciences) and FITC-labeled mouse anti human HLA-DR antibody (clone: G46-6, BD Biosciences). MDSC will be defined by flow cytometry as CD11b⁺ CD33^{+/low} HLA-DR^{-/low} cells.

9.2 Comparable Methods

This study will employ procedures that have been validated previously for clinical use.

10. SPECIMEN MANAGEMENT

10.1 Laboratories

Clinical laboratory analyses will take place at each Participating Organizations' CAP-certified laboratory.

Immunology analyses will take place in the laboratory facilities overseen by [name]. at the University of Pittsburgh:

[name]

[contact] or [contact]; [contact]; Email: [contact]

10.2 Collection and Handling Procedures

10.2.1 Specimen Kits and Shipping Instructions

Research blood kits will be provided by BAP Kit Building (Biospecimen Accessioning and Processing Core Facility). Collection, handling, and shipping instructions will be included with each kit. Participating Sites may obtain research blood kits by faxing the Supply Order Form to the number provided (found in the Forms Packet). At least two weeks should be allowed to receive the shipping kits. Kits will be sent via FedEx® Ground at no additional cost to the participating institutions. They will not be forwarded by FedEx® rush delivery service unless the participating institution provides their own FedEx® account number. CPN will not cover the cost for rush delivery of kits.

Because charges are incurred for all outgoing kits, a small, but sufficient, supply of specimen collection kits should be ordered prior to participant entry.

- ALL sections of the requisition form and specimen collection labels must be completed and legible.
- Blood specimens should be sent over night via FedEx® on cold packs Monday Thursday ONLY.
- All samples must be shipped to the address provided on the specimen shippers (See Section 10.2.2).

All samples will be shipped in compliance with the International Air Transport Association (IATA) Dangerous Goods Regulations.

10.2.2 Research Blood Specimens

Research blood specimens will be collected according to the table in Section 7.1. Blood specimens for the immune assays must be collected **M-Th only** and shipped overnight for next day analysis. Detailed instructions for collecting, processing, labeling, and shipping the specimens can be found in the instructions provided in each blood specimen kit.

Immune Assays: Heparinized whole blood (4 green-topped tubes) collected at all locations will be shipped to the University Of Pittsburgh School Of Medicine. Trained laboratory personnel will receive

MAY2016-08-01 Version 5.0, Amendment 6 January 25, 2021

and record the specimens, and will also be responsible for processing the blood into plasma and PBMCs. PBMCs will be frozen at -70 to -80°C in human serum with 20% DMSO and plasma will be frozen at -20°C. Lab personnel will run ELISA assays for anti-MUC1 IgG and FACS analysis of % MDSC. Approximately 50% of plasma and 25% of the live cells will be shipped to the Biorepository at the Mayo Clinic for storage and later release when requested for analyses of MUC1 immune response (T-cells +/-cytokine responses), as well as additional biomarker studies.

Blood specimens for immune assays will be sent to:

[name], [name]

[contact] or [contact]; [contact]; Email: [contact]

For tracking purposes, participating organizations will telephone or email [name] to inform the lab that specimens are being sent to the University of Pittsburgh.

[name],

Email: [contact]

Mandatory blood specimen for secondary and exploratory endpoints, as well as optional research blood collection (for individuals who consent to providing blood for future unspecified research) will take place at Baseline/Screening and at Week 24. See the table on the following page for details.

BAP kits will be available for this blood collection utilizing the MAY2016-08-01 BAP Kit Supply Order Form. If are questions or problems with the BAP kits, please email: mccc/[contact]

Biospecimen Summary

Specimen	Timepoints	Processing	Shipping		
Mandatory clinical blood specimen for safety/ Toxicity monitoring. Specimen specifications per local lab SOPs.	Baseline/Screening and Weeks 2, 4, 10, 12, and 24	Process according to local lab SOPs	Not applicable		
Mandatory clinical urine specimen for cotinine (nicotine and metabolites). Specimen specifications per local lab SOPs.	Baseline/Screening and Weeks 12 and 24.	Process according to local lab SOPs	Not applicable		
Mandatory research blood specimen for immune assays: Whole blood, Sodium heparin four (4) green topped tubes	Baseline/Screening, Week 2, Week 4, Week 12, and Week 24	No processing; maintain ambient temperature.	Mayo will ship ambient overnight via FedEx [™] M-Th to U Pitt. U Pitt will transport ambient on the day of collection to [name] lab.		
 Mandatory specimen for secondary and exploratory endpoints. One (1) Gold SST tube will be collected for hsCRP. All remaining blood tests for secondary and exploratory endpoints will utilize specimens remaining after the immunological assays are complete. 	Baseline/Screening and Week 24	Process SST tube into serum and aliquot. Label as serum. Freeze at a minimum of -20°C.	U Pitt will ship frozen on dry ice overnight via FedEx [™] to BAP lab for accessioning and storage at -80°C. Mayo will transport on dry ice on the day of collection to BAP for accessioning and storage at -80°C.		
Optional blood specimen for future research: One (1) 10-mL EDTA purple-topped tube and one (1) 10-mL red/gold topped tube.	Baseline/Screening and Week 24	Process EDTA purple topped tube into plasma and buffy coat; Process red/gold topped tube into serum. Aliquot, label, and freeze at a minimum of -20°C. Make sure labels distinguish serum versus plasma versus buffy coat.	U Pitt will ship frozen on dry ice overnight via FedEx [™] to BAP lab for accessioning and storage at -80°C. Mayo will transport on dry ice on the day of collection to BAP for accessioning and storage at -80°C.		

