6.8.2 Registration

- 6.8.2.1 To register a participant, the participating site will send the completed, signed, and dated Registration Eligibility Checklist to the CPN Registration Office (Email: [contact]; [contact]). The CPN Registration Office will enter the information into the CPN-hosted database. For randomization details, see Section 13.2.
- 6.8.2.2 Intervention on this protocol must commence at a CPN institution under the supervision of a CPN clinician.

6.8.2.3 Intervention cannot begin prior to Registration and must begin ≤ 14 days after Registration.

6.8.2.4 Descriptive Factors:

- Participating organization: University of Pittsburgh versus Mayo Clinic
- Gender: Male versus female
- Smoking status: Current versus former

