13.5 Secondary Objectives, Endpoints, Analysis Plans

- To explore potential differences, if any, in the immunogenicity of the vaccine (as assessed at weeks 12 and 24 by the IgG anti-MUC1 antibody titer ratio) in current vs. former smokers. We will thus continuously monitor enrollment to the trial by smoking status. Once 15 participants are enrolled, a breakdown of enrollment by smoking status will be shared with the study team. Based on the smoking status distribution, the study team will make a decision to either continue the study as is, or restrict enrollment to either the current or the former smokers in order to have at least 15 participants each within the former and current smoker categories.
- To evaluate pre-vaccination levels versus post-vaccination (Week 12) levels of circulating myeloid derived suppressor cells (MDSC) and correlate with the ability to respond to the vaccine. For this analysis, we will summarize the data using descriptive statistics and graphical methods (i.e. boxplots, scatter plots, etc.). For continuous MDSC data vs. response data, we will use t-tests or Wilcoxon Rank-Sum tests (for non-normal data). For the associations of 2 continuous variables, we will use linear regression, the correlation coefficient, and scatter plots.

In addition, as exploratory endpoints we will also assess:

- The relationship between COPD status at pre-registration and immune response in current versus former smokers. In individuals with COPD, the severity of airflow obstruction will be measured by the pulmonary function tests as per the GOLD classification
- Whether or not changes in immunogenicity in individuals with COPD corresponds to different circulating MDSC levels
- The impact of the MUC1/Poly-ICLC vaccine on inflammation-related high sensitivity C-reactive protein (hsCRP) and interleukin-6 (IL-6)
- The ability to successfully vaccinate with MUC1/Poly-ICLC vaccine depending on baseline hsCRP and IL-6 levels.

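### Processing delay for the MDSC assay is tied to site, but the comparison of pre-vaccination MDSC with response has no site-adjusted analysis beside it.

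*Combined protocol and SAP*

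**What the plan says.** **Handling.** The immune-assay row of the Biospecimen Summary (Section 10.2.2) allows no processing before arrival and then gives two routes: "Mayo will ship ambient overnight via FedEx" to Pittsburgh, and "U Pitt will transport ambient on the day of collection to" the laboratory. Section 9.1 describes the same two routes: "Upon receipt of the overnight shipment or immediately after collection, heparinized blood will be centrifuged over a density gradient". The MDSC percentage is measured on the cells from that separation after freezing: "PBMC will be thawed and stained with APC-labeled mouse anti-human CD11b antibody". The difference in delay arises before freezing, so later batch testing cannot remove it.

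**Conflicting text.** The narrative of Section 10.2.2 requires immune-assay blood to be "shipped overnight for next day analysis" and makes no exception for Pittsburgh. Section 10.2.1 calls for cold packs, whereas the table says ambient.

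**Analysis.** Section 1.2 sets the secondary objective: relate the pre-vaccination MDSC level to the ability to respond. For this, Section 13.5 says "we will use t-tests or Wilcoxon Rank-Sum tests (for non-normal data". Two continuous variables get linear regression, a correlation coefficient and scatter plots. Neither 13.5 nor 13.10 names a site term or a site sensitivity analysis. Section 13.2 gives stratification as not applicable. Section 6.8.2.4 does record site as a descriptive factor: "Participating organization: University of Pittsburgh versus Mayo Clinic".

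**The concern.** The pre-vaccination MDSC level is compared between people, and each person's delay is set by where they enrolled. If delay moves the measured percentage, two things can happen.

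- With similar response rates at the sites, the shift is extra noise in both groups, and a true association is harder to see.
- With different response rates, the shift is a confounder. It can produce an association that is not there, enlarge a real one, or cancel it.

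MDSC carries much of the trial's rationale. Section 2.2 attributes non-response in the completed colon-adenoma study to raised MDSC, and that study ran at Pittsburgh. This trial adds a second site whose blood travels overnight.

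A difference in response between sites is plausible but not established. Section 13.4 calls the population heterogeneous, Section 3 links COPD to raised MDSC, and Section 4.6 has each site recruiting under its own plan.

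**Working it through.** **Step 1: the plan's nearest figure.** No power is stated for the MDSC analysis. The nearest figure is in Section 13.4: 96% power with N = 40, 15% versus 40%, two-sided 0.05. By the one-sample normal approximation:

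Φ((0.25·√40 − 1.96·√(0.15·0.85)) / √(0.40·0.60)) = Φ((1.581 − 0.700)/0.490) = Φ(1.80) = 96.4%.

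This reproduces and is not in dispute. It supplies N = 40 and a response rate near 40%, so about 16 responders and 24 non-responders.

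**Step 2: assumptions.** The documents give no processing shift, site split or site-specific response rate. Assumed here: a constant additive shift δ of 0 to 1.5 SD at one site, 20 participants per site, and a true responder difference of either 0 or 0.9 SD.

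**Step 3: equal response rates (40% at both sites).** The shift raises the within-group variance from 1 to 1 + δ²/4. The effective difference is 0.9/√(1 + δ²/4), and the noncentrality multiplies it by √(16·24/40) = 3.098. With t critical value 2.024 (38 df):

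- δ = 0: 0.900 × 3.098 = 2.79; Φ(2.79 − 2.024) ≈ 78%
- δ = 1.0: 0.805 × 3.098 = 2.49; Φ(0.47) ≈ 68%
- δ = 1.5: 0.720 × 3.098 = 2.23; Φ(0.21) ≈ 58%

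Simulation (4,000 to 5,000 trials per setting) agrees:

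| Power, true difference 0.9 SD | δ = 0 | 0.5 | 1.0 | 1.5 |
|---|---|---|---|---|
| t-test | 77% | 74% | 68% | 56% |
| Wilcoxon | 73% | 72% | 63% | 52% |
| Linear model with site | 76% | 75% | 76% | 76% |

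The van Elteren test stays at about 71-73%. The simulation standard error is about √(0.7·0.3/4000) = 0.7 points, so 1-2 point differences are noise; repeat runs at δ = 0.5 gave 69-72% for the rank test. With no true difference, false positives stay near 5% at every δ.

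**Step 4: unequal response rates.** The bias in the unadjusted difference is δ × [P(site with shift | responder) − P(site with shift | non-responder)]. With 25% response at the shifted site and 55% at the other, this is δ × [0.25/0.80 − 0.75/1.20] = δ × (0.3125 − 0.625) = −0.31δ. The simulated bias at δ = 1 was also −0.31 SD.

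| False positives, no true difference | δ = 0.5 | 1.0 | 1.5 |
|---|---|---|---|
| 50% vs 30%, t-test | 5.8% | 8.1% | 11.4% |
| 55% vs 25%, t-test or Wilcoxon | 7-8% | 13-14% | 21-22% |
| 60% vs 20%, t-test | 9.5% | 21.4% | 34.8% |
| Any of these, linear model with site | about 5% | about 5% | about 5% |

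At 45% versus 35% with δ = 1.0, the unadjusted rate is only 5-6%.

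**Step 5: masking.** If the site that reads higher also responds more (55% vs 25%) and responders truly have lower MDSC by 0.9 SD, rank-test power falls to about 30% at δ = 1.0 and 14% at δ = 1.5. The linear model with site keeps about 71%.

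**Step 6: cost of adjusting when there is no shift.** With equal response rates, the t-test has 77% against 75% for the linear model with site, and the Mann-Whitney test 73% against 71% for van Elteren. At 55% versus 25% the cost is about 6-8 points; for the rank tests, about 74% against 66%.

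**The case against.** **No documented harm.** No section says that overnight ambient holding changes the MDSC percentage, in which direction, or by how much. This stands. A reader might infer that the Mayo values are known to be biased; the documents do not support that. A false association needs both a shift and a response difference between sites, and the larger rates above come from large values of both.

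**Adjustment is not free and can remove signal.** This also stands. It costs power, most where response differs by site. If the sites differ in COPD or smoker mix, part of the site difference in MDSC may be the biology under study, and a site term removes it along with any artefact. A reader might infer that the site-adjusted test should replace the planned one; these costs argue against it.

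**Own-control design.** Section 9.1 says each participant is their own control, but that sentence concerns antibody titers. A constant additive shift does cancel in each person's absolute MDSC change from baseline to Week 12. It does not cancel in the between-person comparison of pre-vaccination level.

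**Conflicting shipping text.** If the Section 10.2.2 narrative were followed at both sites, the difference in delay would largely disappear. Section 9.1 and the table both describe two routes, but the conflict means that the confounding depends on which text sites followed.

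**Pilot status.** The analysis is secondary, and Section 13.10 treats notable translational results as prompts for further study. That limits the weight of the point, though a possible handling artefact is a poor prompt.

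**Conclusion.** The point holds as a gap in the plan. By Section 9.1 and the Biospecimen Summary, processing delay is tied to site, and the between-person MDSC comparison in Section 13.5 takes no account of it.

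The size is a sensitivity range, not an estimate of actual bias. It rests on N = 40, an equal site split, a constant additive shift of at most 1.5 SD and, for the power figures, a true 0.9 SD difference. Under equal response rates the harm is lost power only, small at 0.5 SD and about 10 and 21 points for the rank test at 1.0 and 1.5 SD (73 − 63 and 73 − 52). False positives rise only if response also differs by site.

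A reader might extend this to the whole secondary objective or to the primary endpoint. Neither follows: absolute within-person MDSC change is unaffected by a constant additive shift, and the power of the primary immunogenicity test does not depend on MDSC. The change is worth making because it is cheap and protects a named secondary objective.

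**What to change.** 1. In Section 13.5, and in 13.10 for between-person analyses of MDSC level, report a site-adjusted analysis alongside the planned t-test, Wilcoxon test or regression. Use a linear model with a site term or a van Elteren test stratified by site, and name the choice in advance.
2. Show MDSC by site, overall and by response.
3. State how the two results will be read together. An association that disappears after adjustment is possibly due to handling; it may also reflect real differences in case mix or the power given up, which is why the unadjusted result stays beside it.
4. Reconcile the shipping text: the narrative of 10.2.2 with 9.1 and the Biospecimen Summary on same-day or overnight handling at Pittsburgh, and 10.2.1 with the Biospecimen Summary on cold packs or ambient.

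This needs no new samples, visits or participants: site is already recorded, and the linear model spends one degree of freedom. The power cost set out above falls on the adjusted analysis only.

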10.3 Shipping Instructions

All samples will be shipped in compliance with the International Air Transport Association (IATA) Dangerous Goods Regulations.

10.4 Biospecimen Banking

Optional blood specimens collected at baseline and Week 24, as well as any blood specimens remaining after the analyses for the primary and secondary endpoints are complete will be stored for future research, including analyses for exploratory endpoints and future unspecified research.

MAY2016-08-01 Version 5.0, Amendment 6 January 25, 2021

At study completion, remaining frozen biologic specimens will be labeled (study number, participant ID number, specimen type, specimen number, date of collection) batched, and shipped (overnight, M-Th only) for short-term storage to:

Biospecimens Accessioning and Processing (BAP) [name]

NCI reserves the option to either retain or relinquish ownership of the unused biologic specimens. If NCI retains ownership of specimens, the Contractor shall collect, verify and transfer the requested biologic specimens from the site to a NCI-specified repository or laboratory at NCI's expense.

Biologic specimens collected during the conduct of each clinical trial that are not used during the course of the study will be considered deliverables under the contract and thus the property of the NCI. At study completion, NCI reserves the option to either retain or relinquish ownership of the unused biologic specimens. If NCI retains ownership of specimens, the Contractor shall collect, verify and transfer the requested biologic specimens from the site to a NCI-specified repository or laboratory at NCI's expense.

11. REPORTING ADVERSE EVENTS

DEFINITION: AE means any untoward medical occurrence associated with the use of a drug in humans, whether or not considered drug related. An AE can therefore be any unfavorable and unintended sign), symptom, or disease temporally associated with participation in a study, whether or not related to that participation. This includes all deaths that occur while a participant is on a study.

Please note that all abnormal clinical laboratory values that are determined to be of clinical significance based on a physician's assessment are to be reported as AEs. Those labs determined to be of no clinical significance or of unknown clinical significance (per the physician's assessment) should not be reported as AEs. Any lab value of unknown clinical significance should continue to be investigated/followed-up further for a final determination, if possible.

Since there is considerable physiologic variability in the Pulmonary Function Tests (PFTs) done at two different time points, to report statistically and clinically relevant AEs related to PFTs done at week 24 the following definitions will be used:

A. For a participant with normal PFTs at baseline (normal PFTs as defined by FEV1 >80% predicted and FEV1/FVC ratio ≥ 0.7)

*Any decline in FEV1 done after vaccination series of ≥ (equal or higher) 12% and ≥ (equal or higher) 200cc as compared to baseline FEV1 would be reportable regardless of its relatedness to the study vaccine.

B. For a participant with abnormal PFTs known previously or determined at the time of baseline testing (abnormal PFTs as defined by FEV1 ≤ (equal or less) 80% and FEV1/FVC ratio < 0.7)
*Any decline in FV1 done after vaccination series of ≥ (equal or higher) 20% and ≥ (equal or higher)
330cc as compared to baseline FEV1 would be reportable regardless of its relatedness to the study vaccine.

A list of AEs that have occurred or might occur can be found in §6.2 Reported Adverse Events and Potential Risks, as well as the Investigator Brochures.

